Take Action for Asthma Control Study - Developing pictorial asthma action plans to promote self-management and health in rural youth with asthma

NCT03187119

5/29/2020

Study Protocol

Title: Take Action for Asthma Control Study - Developing pictorial asthma action plans to promote self-management and health in rural youth with asthma

Funding: US DHHS-HRSA-Maternal and Child Health Bureau (R40MC28320) for 2015-2018)

Principal Investigator: [name], Professor in Department of Psychology at West Virginia University; Office [contact]; Email: [contact]

Background: Asthma, the most common chronic illness in children, is characterized by symptoms of wheezing, coughing, chest tightness, and shortness of breath. When poorly managed, asthma can be associated with negative social and health outcomes (Akinbami, Moorman, & Liu, 2011; Akinbami, & Schoendorf, 2002). Asthma action plans (AAPs) are individualized treatment plans, arranged in a stoplight format, that specify daily asthma care activities as well as instructions for adjusting medication or seeking emergency medical help in response to symptoms. Regular use of an AAP has been associated with improved outcomes such as adherence to daily inhaler use and fewer symptomatic days and nights (Bhogal, Zemek, & Ducharme, 2006). However, written AAPs are targeted at a 7th to 9th grade reading level and are dense with text, which significantly constrains their utility and may contribute to health disparities. Rural families with literacy issues are particularly at risk. A critical need exists to develop a simpler format for AAPs.

Overall Aim: The overall aim of this pilot RCT is to develop a symptom-based, computer-generated pictorial AAP (PAAP) and to investigate acceptability and feasibility in a pilot randomized controlled trial (RCT). The PAAP will be comprised primarily of images, with minimal words or phrases, to direct the family regarding the child's asthma regimen.

Specific Aim # 1 – Determine the relative

of pictorial & written AAPs. Our working hypothesis is that relative to usual care (Written AAP), Pictorial AAP will produce superior clinical and behavioral outcomes: (a) better treatment plan knowledge for caregiver and patient; (b) higher daily adherence rates to preventive medication (via electronic monitoring); and (c) better health outcomes (i.e., report of better asthma control & higher *lung functioning* or spirometry scores). This hypothesis is based in part on research findings indicating that use of pictures in health education markedly increases recall of information through simpler and more salient cues.

Specific Aim # 2 – Evaluate provider and family acceptability of pictorial AAP. Based on existing literature, we expect that the Pictorial AAP will be easy and user-friendly for providers to offer as well as patients and families to use. Consequently, our working hypothesis is that patient and caregiver satisfaction (e.g., perceived ease of use, benefits) survey scores will be significantly higher for the Pictorial AAP than for the Written AAP group.

Specific Aim # 3: Identify whether parent health literacy and youth literacy levels are associated with treatment outcome. Pearson (parametric) or Spearman (non-parametric) correlations will be used as appropriate to assess the association between parent health literacy and youth literacy to changes in knowledge, adherence, and health outcome, as well as caregiver and patient satisfaction, within and between AAP groups. Given that research suggests the use of graphics and images improves comprehension of medical information, it is anticipated that rural youth, particularly with lower literacy levels, will benefit significantly from a simpler, “image rich” pictorial AAP.

Design: Pilot Randomized Controlled Trial

Young people aged 8-17 were randomly assigned to one of two groups (pictorial vs. written AAP, i.e. usual care) for 6 months. The Written AAP (WAAP) group received a personalized, text-based AAP. The WAAP is consistent with national practice guidelines [5] and recommended as standard care for patients with asthma. The proposed study will use the written AAP published by the National Heart Lung and Blood Institute (NHLBI) (Available at: https://www.nhlbi.nih.gov/files/docs/public/lung/asthma_actplan.pdf). Providers (not researcher) completed the WAAP with the child's prescribed medications and specific asthma care regimen. The provider reviewed the WAAP with the child and caregiver.

The Pictorial AAP (PAAP) group received a largely pictorial version of their AAP (with only brief & simple text). Its content was personalized to their prescribed regimen and comparable to that of the written AAP (e.g., asthma regimen divided into stoplight-color zones); however, it used conventional pictures and symbols to represent what, when and how medications should be taken. Providers accessed the PAAP software program in clinic, after evaluating the patient, and selected options from dropdown menus to tailor the PAAP to the particular patient's asthma regimen. The PAAP was provided to the participant, another was saved in the participant's online medical record, and a third was kept in their research record. The provider reviewed the PAAP with the child and caregiver.

It is hypothesized that the use of the PAAP will produce better AAP knowledge, higher objectively measured adherence rates to daily asthma medication, and better health outcomes, such as asthma control.

Methods:

This pilot RCT began data collection in May 2017 and continued through May 2018. A total of 45 youths and their families were recruited. Data was collected at four time points: baseline (recruitment), 1-month, 3-months, and 6-months. At baseline, caregivers completed a general information form on demographics and medical history, as well as measures to assess health status (Asthma Control Test), and health literacy (S-TOFHLA and Asthma Numeracy Questionnaire). Patients completed measures to assess health status (Asthma Control Test), health literacy (S-TOFHLA) and reading comprehension (WIAT-III), and complete pulmonary function testing (spirometry). Qualitative methods were used to gather acceptability and feasibility data. Participants in both groups were provided with their first canister or diskus of medication in order to attach the electronic adherence monitor at baseline. Participants refilled with medications they purchase as needed for the remainder of the study. One month after initial visit, families were called to complete the Asthma Control Test and study-specific satisfaction survey. Three months after initial visit, families returned to clinic for follow up with the physician and to complete the Asthma Control Test, AAP knowledge interview, and pulmonary function testing (patient only). Six months after initial visit, families returned to clinic for follow up with the physician and to complete the Asthma Control Test, AAP knowledge interview, satisfaction survey, spirometry (patient only), and to review adherence data and return the inhaler monitor. Six families completed follow up measures at 3 months due to time constraints.

The findings of this study will be relevant to research and practice with rural youths with asthma, as well as families with significant literacy issues. A novel and innovative stakeholder-led approach was used in this study to develop a more accessible and effective approach to asthma education in pediatric settings. The process and findings of this study will be widely disseminated and guide improvements to the PAAP for use in future research and practice, including the possible development of an "app" version of the PAAP.

Study Analysis Plan

All analysis was conducted using SAS 9.4. Descriptive analysis was conducted on baseline measures for both the total sample, and by treatment group. Frequency and valid percentages were used to describe categorical data, means and standard deviations for continuous data, and medians and interquartile range for non-normal continuous data. Group differences were tested by chi-square, Fisher's exact, Mann-Whitney, or t-test as appropriate for variable type, with odds ratios (OR) and 95% CI of the OR, means by group and t-statistic, or mean score ranks and Z-statistic reported.

Generalized linear mixed model (GLIMMIX) with multinomial response distribution and a cumulative logit link function were used to analyze the daily adherence data, in order to model the ordinal outcome measure (0%, 25%, 50%, 75%, and 100% adherence) over time. Multiple covariance structure models were tested, with an unstructured matrix best fitting by AIC. Because adherence changed depending on prescription, the models were tested by both interaction of prescription and by stratification. Sensitivity analysis was also run for 3 months or less data and compared to the full 6 month dataset. Fixed effects were reported. Generalized linear mixed model (GLIMMIX) with binary response distribution was also conducted for the binary outcome of ACT cut-off ≥ 19 .

Linear mixed models with restricted estimation maximum likelihood estimation and Kenward-Richardson adjustment for the degrees of freedom were used for the continuous outcome data. Pre-post analysis included combining 3 month and 6 month time points for outcome measures where the final time point was 3 instead of 6 months. Time was treated as categorical for these pre- post- time points; otherwise time was treated as continuous variable. Time, Group, and Time by Group interaction effects were included in the model. Random effects statement included the time, with participants listed by ID. Different covariance structures and intercept inclusion were tests; AIC was used to determine best model fit with the best fitting model including no intercept and an unstructured covariance matrix. Fixed effects are reported. Sensitivity analysis was also run by including days in the study for those post-outcomes where some participants have 3 months or less data and compared to the full 6 month dataset.

Finally, equivalence testing was conducted for all continuous outcomes, assuming that results that fall within an SD unit difference would indicate that PAAP is as good as guideline-recommended care (WAAP) with sufficient power. The overall stability of the effect of the treatment response was demonstrated utilizing the F test for equivalence of the effect of psi-squared, a standardized measure of difference between groups/time point means and an overall (across groups and time points) mean. This was be assessed utilizing output from the best-fitting general linear mixed model and by testing whether this psi-squared effect size measure falls in the critical region [6].

References

1. Akinbami, L. J., & Schoendorf, K. C. (2002). Trends in childhood asthma: Prevalence, health care utilization, and mortality. *Pediatrics*, 110(2), 315-322.
2. Akinbami, L. J., Moorman, J. E., & Liu, X. (2011). Asthma prevalence, health care use, and mortality: United States, 2005-2009 (Report No. 32). Atlanta, GA: National Health Statistics Reports, Centers for Disease Control and Prevention; <http://www.cdc.gov/nchs/data/nhsr/nhsr032.pdf>. Updated January 12, 2011. Accessed May 4, 2014.
4. Forbis, S. G., & Ailigne, C. A. (2002). Poor readability of written asthma management plans found in national guidelines. *Pediatrics*, 109, e52.
5. National Heart, Lung, and Blood Institute (2007). National Asthma Education and Prevention Program (NAEPP) Expert Panel Report 3, *Guidelines for the Diagnosis and Management of Asthma* (NIH Publication No. 08-4051).
6. Wang, F., & Amrhein, J. (2016, April 18-21). *Equivalence Tests*. Paper presented at the Proceedings of the SAS®Global Forum 2016., Las Vegas, NV

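### Aim 3 correlates youth literacy with outcomes across ages 8 to 17 without allowing for age, so pooled and within-arm correlations for any score not age-standardised can reflect age instead of literacy

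*Combined protocol and SAP*

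**What the plan says.** Specific Aim # 3 names the method: "Pearson (parametric) or Spearman (non-parametric) correlations will be used as appropriate to assess the association between parent health literacy and youth literacy". It is applied "to changes in knowledge, adherence, and health outcome, as well as caregiver and patient satisfaction, within and between AAP groups". No covariate, age stratum or partial correlation is mentioned.

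The Design section gives the population: "Young people aged 8-17 were randomly assigned to one of two groups". Methods lists the youths' baseline literacy measures as "health literacy (S-TOFHLA) and reading comprehension (WIAT-III"), without saying whether raw or age-standardised scores are analysed.

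The Study Analysis Plan does not describe the Aim 3 correlations, so nothing there fills the gap. Its linear mixed models contain no age term either: "Time, Group, and Time by Group interaction effects were included in the model". Age should already be held, since at baseline "caregivers completed a general information form on demographics and medical history". The sample is small: "A total of 45 youths and their families were recruited".

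**The concern.** A reading score that is not standardised for age will generally rise between ages 8 and 17. The Background section itself expresses reading difficulty in school grades (7th to 9th for written plans), and this age range straddles that level. Plan knowledge, responsibility for the inhaler and adherence may also vary with age; that is plausible, but the documents do not say so. If both links exist, a simple correlation mixes the two influences. It could show a literacy association where there is none at a given age, or hide a real one. Literacy is not randomised, so allocation does not remove this from correlations computed across children of different ages.

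What is at stake is the reading of Aim 3. The protocol expects youths with lower literacy in particular to benefit from the pictorial plan, and it intends the findings to guide later versions. If the signal is really age, that guidance could be aimed at poor readers when it should be aimed at younger children, or the reverse. The randomised comparison of the two plans is not affected.

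**Working it through.** The plan gives no power, alpha or correlation figure for Aim 3, so there is nothing to reproduce. What follows is an illustration.

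**Inputs from the documents.** n = 45 (Methods); ages 8 to 17 (Design); simple correlations (Specific Aim # 3).

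**Assumed inputs.** Age-literacy correlation 0.6 to 0.8; age-outcome correlation 0.2 to 0.4 in size, of either sign; no literacy effect at a given age; two-sided 5% level; about 22 youths per arm, because arm sizes are not given.

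**Step 1: expected unadjusted correlation.** With no literacy effect at a given age, r = r(age, literacy) × r(age, outcome).

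**Step 2: chance of p < 0.05.** By Fisher's z, with m = atanh(r) × √(n − 3), the chance is 1 − Φ(1.96 − m) + Φ(−1.96 − m). Here √42 = 6.48 for all 45 youths and √19 = 4.36 for one arm. Only the size of r matters.

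| Age-literacy × age-outcome | Size of r | n = 45 | n = 22 |
|---|---|---|---|
| 0.6 × 0.2 | 0.12 | 12% | 8% |
| 0.7 × 0.3 | 0.21 | 28% | 15% |
| 0.7 × 0.4 | 0.28 | 46% | 24% |
| 0.8 × 0.4 | 0.32 | 58% | 30% |
| 0 × any (age-standardised) | 0 | 5% | 5% |

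**Step 3: check by simulation.** In 20,000 simulated trials of 45 youths with age spread evenly over the range, and correlations of 0.7 and 0.4, the unadjusted correlation averaged 0.28 and reached p < 0.05 in about 47%. The correlation with age partialled out averaged about 0.00 and did so in about 5%.

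**Step 4: masking.** Take a real standardised literacy effect of +0.3, a direct age effect of −0.4 and an age-literacy correlation of 0.7. The unadjusted correlation is then about 0.3 + 0.7 × (−0.4) = 0.02.

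**Step 5: which outcomes are exposed.** Aim 3 speaks of changes in knowledge, adherence and health outcome. However, Methods has the adherence monitor attached at baseline, so no earlier adherence is described, and it lists the knowledge interview only at 3 and 6 months. Satisfaction is not a change score. These three are in effect follow-up levels, so no baseline value is subtracted that could remove an age effect. Asthma control and spirometry do have baseline values, and their changes may be less related to age.

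**Step 6: between-arm comparison.** If age acts alike in both arms, each arm's correlation shifts by the same expected amount (for example 0.28 − 0.28 = 0), so the contrast is largely unaffected. An age-by-treatment effect would not cancel.

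**Step 7: price of partialling.** For a fixed residual variance, the standard error of the literacy slope is multiplied by 1/√(1 − r²), where r is the age-literacy correlation: 1/√0.64 = 1.25 at 0.6 and 1/√0.36 = 1.67 at 0.8. With a real standardised literacy effect of 0.3, no direct age effect and n = 45, power falls from about 52% unadjusted to about 36%, 30% or 22% at age-literacy correlations of 0.6, 0.7 or 0.8.

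**The case against.** The strongest objection concerns the question being asked. Aim 3 is about literacy levels, and its rationale is absolute readability: a child who reads poorly because of being young faces the same barrier as an older poor reader. Partialling out age replaces reading level with reading level relative to age peers, and removes any part of an age effect that works through reading. This stands. A reader might infer that the age-partialled correlation should be the main Aim 3 result; the documents do not support that, because the unadjusted correlation answers a legitimate question.

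The cost objection also stands. The conditions that make the bias large also make the adjusted estimate imprecise, which matters with 45 youths.

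A third objection is that most Aim 3 outcomes are called changes, and age may be only weakly related to change over 3 to 6 months. This holds in part, for asthma control and spirometry. It does not dispose of adherence, knowledge or satisfaction.

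A reader might also infer that randomisation gives no protection anywhere in Aim 3. That goes too far, since an age effect common to both arms largely cancels in a between-arm contrast. It does not cancel in the pooled or within-arm correlations.

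Finally, the problem is conditional: if the scores analysed were age-standardised, it is near zero for those scores. The documents leave the score type open, so this limits the concern without removing it.

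**Conclusion.** The point holds in a limited form. Specific Aim # 3 neither allows for age nor states the score type, so for any youth literacy score that is not age-standardised a pooled or within-arm correlation cannot by itself be attributed to literacy independent of age. Under the assumed correlations, the chance of a significant result with no literacy effect is about 12% to 58% with all 45 youths and about 8% to 30% in an arm of about 22. The upper ends need both assumed correlations at the top of their ranges.

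A reader might infer that the Aim 3 results are in fact confounded by age. The documents do not show that: they give no correlation of age with either literacy or outcome, and they leave open that standardised scores were used. Nor does the point carry over to parent health literacy or to the randomised comparison. It is a cheap improvement to the interpretation of one aim of a pilot trial.

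**What to change.** State for S-TOFHLA and WIAT-III whether raw or age-standardised scores are analysed. For each youth literacy score that is not age-standardised, report the age-partialled Pearson or Spearman correlation beside the planned unadjusted one. Attribute an association to literacy independent of age only if it persists after partialling; the unadjusted value still describes absolute reading level. Leave the parent-literacy correlations as planned.

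This takes one PARTIAL statement in the SAS correlation procedure, using age from the baseline form, and no new data. The statistical cost is one degree of freedom and a materially less precise literacy effect: a slope standard error about 1.25 to 1.67 times larger if the age-literacy correlation is 0.6 to 0.8. A partial correlation that is not significant should therefore not be read as showing that literacy has no effect.

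### Aim 3 correlates literacy with change in adherence, but no pre-plan adherence is described, and a change within follow-up cannot show a constant literacy effect

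*Combined protocol and SAP*

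**What the plan says.** Specific Aim # 3 proposes to "assess the association between parent health literacy and youth literacy to changes in knowledge, adherence, and health outcome", within and between the two plan groups. The method is stated as "Pearson (parametric) or Spearman (non-parametric) correlations will be used as appropriate". Such a correlation needs one adherence value per child. The documents do not say how that value is formed or what the change is measured from.

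Specific Aim # 1 (b) states adherence as a level, "higher daily adherence rates to preventive medication (via electronic monitoring", and gives no time window.

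On timing, the Methods say that participants in both groups were "provided with their first canister or diskus of medication in order to attach the electronic adherence monitor at baseline", and that at six months families came, among other things, "to review adherence data and return the inhaler monitor". They also say: "Data was collected at four time points: baseline (recruitment), 1-month, 3-months, and 6-months". The baseline measures listed are demographics, medical history, the Asthma Control Test, literacy and numeracy measures, reading comprehension and spirometry. No adherence measure or monitored run-in is among them.

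No date is given for issue of the plan. The Design section says that the young people "were randomly assigned to one of two groups (pictorial vs. written AAP, i.e. usual care) for 6 months", and then, for the pictorial arm, "Providers accessed the PAAP software program in clinic, after evaluating the patient".

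The Study Analysis Plan models daily adherence over time as a five-level ordinal outcome in a generalized linear mixed model. It handles prescription by interaction and by stratification, and adds a sensitivity analysis limited to data up to 3 months. It defines no adherence change and does not mention the Aim 3 correlations.

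**The concern.** Two aims use the same monitored behaviour in different forms. That alone is not a fault. The difficulty is that the Aim 3 form, a change, has no definition and no pre-plan reference in the design as described. An analyst has to fall back on a change inside the follow-up period, and such a score removes any literacy difference that is present throughout.

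Literacy is the rationale for the trial, and adherence is its one electronically monitored behaviour. If children with lower literacy take fewer doses from the first day to the last, a within-follow-up change would probably show nothing. A reader would have no warning that the score could not have shown it.

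**Working it through.** **Step 1. Is there a pre-plan value?** The Methods place the start of monitoring at baseline and its end at the six-month visit. Allocation also runs for six months. Plans were completed in clinic by the provider. Together these imply that monitoring and plan began at about the same time. This is an inference, but nothing describes monitored time before the plan or any other baseline adherence measure. Change from a pre-plan value therefore cannot be scored from the data described.

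**Step 2. What does a within-follow-up change measure?** Let adherence of child i at time t be

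A(i,t) = m(t) + b·L(i) + u(i) + s(i)·t + e(i,t),

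where L is literacy, u a stable child effect, s the child's own slope and e noise. Late minus early over an interval d is

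D(i) = [m(late) − m(early)] + d·s(i) + [e(late) − e(early)].

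The term b·L(i) cancels, so Cov(D, L) = d·Cov(s, L). If slopes are unrelated to literacy, this is exactly zero, whatever b is and whether or not adherence declines overall. A fitted slope per child behaves the same way. The zero is exact on an additive scale. On a scale bounded at 0% and 100%, floor or ceiling effects could induce some correlation, but only as an artefact.

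**Step 3. Size.** The documents give no alpha, effect size or power for Aim 3, so there is no planned figure to reproduce. Inputs: n = 45 (Methods). Assumptions: about 22 per arm (equal split), two-sided alpha 0.05, correlation r of literacy with adherence level from 0.3 to 0.5.

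Power = Φ(atanh(r)·√(n−3) − 1.96) + Φ(−atanh(r)·√(n−3) − 1.96); the second term is negligible.

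- r = 0.4, n = 45: 0.4236 × √42 = 2.746; 2.746 − 1.96 = 0.786; power 78.4%.
- r = 0.4, n = 22: 0.4236 × √19 = 1.847; 1.847 − 1.96 = −0.113; power 45.5%.
- Over r = 0.3, 0.4, 0.5: 51.8%, 78.4%, 94.5% pooled; 27.1%, 45.5%, 66.8% in one arm.

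**Step 4. Simulation.** The model was Step 2 without s(i), with 8,000 trials of n = 45 per scenario, stable share of variance 0.5 or 0.7, and mean decline 0 or 0.5 SD. Over r = 0.3 to 0.5, the level was significant in 52% to 95% of trials. The change had mean correlation 0.00 and was significant in 4.6% to 5.3% of trials in all twelve scenarios, which is simply alpha.

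**Step 5. If literacy also acts on the trend.** Assume slope SD 0.15 per six months, monthly noise SD 0.07, early = months 1–2 and late = months 5–6. The slope contributes 0.15 × 4/6 = 0.10. The noise SD of the difference is √(0.07²/2 + 0.07²/2) = 0.07. The SD of the change is √(0.10² + 0.07²) = 0.122, so corr(D, L) = r(slope) × 0.10/0.122 = 0.82·r(slope). Slope correlations of 0.2, 0.3 and 0.4 give about 0.16, 0.25 and 0.33; the Step 3 formula at n = 45 then gives power of about 19%, 37% and 60%.

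**Step 6. Comparing arms.** The standard error of a difference in Fisher-z is √(2/19) = 0.324. For r = 0.4 in one arm and 0 in the other, 0.4236/0.324 = 1.31, and Φ(1.31 − 1.96) gives power of about 26%.

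**The case against.** The best case on the other side has five parts.

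- **The zero is assumed.** It follows from taking slopes to be unrelated to literacy, and no document supports that. This stands. Step 5 shows the change picking up a literacy effect on the trend. In the extreme case where literacy acts only on the trend (slope correlation 0.4, starting level 0), a mean over days 1–90 correlates only about 0.06 with literacy, and change is the better score.
- **Aim 3 is about response, not level.** The aim expects lower-literacy youth to benefit from the pictorial plan. A pooled correlation with level mixes that response with literacy gaps that predate the plan. This stands against a pooled analysis. It does not rescue the change score, and it is met by comparing arms: randomisation balances pre-plan adherence in expectation, so a difference between arms in the literacy–level relation is interpretable without a baseline.
- **Changes may be meant only for knowledge.** Grammatically possible. The natural reading covers all three items, and if a level was meant, the text should say so.
- **Plan issue is undated.** True. If monitoring had preceded the plan, a baseline could exist, but none is described.
- **The six families who finished at 3 months need not be lost.** Correct. Monitoring is daily, so a slope can be computed for all 45. A reader might infer that late minus early is the only possible change and that 6 of 45 (13%) must drop out; the documents do not force that.

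**Conclusion.** The point holds in a limited form. As described, the design gives no pre-plan adherence value, so Aim 3 cannot use change from baseline for adherence. The change that can be computed is insensitive to a constant literacy effect: about 5% rejection, against about 78% pooled and 46% within an arm for the level at an assumed r of 0.4. The cancellation does not depend on the assumed r; the power figures do. They also rest on an equal split, two-sided alpha 0.05 and slopes unrelated to literacy.

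A reader might infer that the trial would wrongly conclude that literacy does not matter for adherence. The documents do not support that: a non-significant correlation in a pilot is not a finding of no effect, and literacy may act partly on the trend. A reader might also infer that Aims 1 and 3 contradict each other. They do not; the defect is an undefined change without a pre-plan reference.

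The same gap affects plan knowledge, since the Methods list the knowledge interview only at 3 and 6 months. Asthma Control Test and spirometry do have baseline values.

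**What to change.** In Specific Aim # 3, define the adherence variable as the level of monitored adherence during follow-up, analysed within each arm and compared between arms.

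- **Preferred:** add literacy and literacy-by-group terms to the daily adherence mixed model in the Study Analysis Plan. This uses all available days from all 45 families, and the model already deals with prescription.
- **If a simple correlation is kept:** use each child's mean daily adherence over a common window, days 1–90, which also covers the six families who finished at 3 months, with the full six-month data as a sensitivity analysis. Aim 1 (b) states no window, so this one must be justified as a common period and not as matching that aim. A raw correlation also ignores prescription.
- **Slope:** report the within-follow-up slope against literacy as secondary, and do not call it change from baseline.
- **Knowledge:** replace change in knowledge by level at follow-up, unless a baseline interview was done; if it was, say so in the Methods.

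The cost is a few sentences and a re-analysis of data already collected. Because data collection had ended, the definition should be labelled as made afterwards. The result describes association with adherence level, not improvement over pre-plan adherence, which the described design cannot measure. Power for the comparison between arms is low (about 26% in Step 6), so estimates and confidence intervals should carry the report.

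### Aim 3 expects lower-literacy youth to gain most from the pictorial plan, but its undefined between-group comparison of correlations yields no PAAP-WAAP difference, or confidence interval, at any literacy level

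*Combined protocol and SAP*

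**What the plan says.** Specific Aim # 3 makes two statements. The objective is to "Identify whether parent health literacy and youth literacy levels are associated with treatment outcome". The expectation that closes the aim is that "it is anticipated that rural youth, particularly with lower literacy levels, will benefit significantly from a simpler", image-based plan.

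The only method named for the aim is Pearson or Spearman correlation of literacy "to changes in knowledge, adherence, and health outcome, as well as caregiver and patient satisfaction, within and between AAP groups". No test, contrast or estimate is attached to the between-groups part.

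The Study Analysis Plan does not mention literacy:

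- **Continuous outcomes:** "Time, Group, and Time by Group interaction effects were included in the model".
- **Adherence:** a cumulative-logit mixed model is used "in order to model the ordinal outcome measure (0%, 25%, 50%, 75%, and 100% adherence) over time". Its only stated effect modifier is prescription, examined by interaction and by stratification.
- **Asthma Control Test (ACT) cut-off:** "Generalized linear mixed model (GLIMMIX) with binary response distribution was also conducted for the binary outcome", with no literacy term stated.

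Methods records two baseline literacy measures for caregivers, "health literacy (S-TOFHLA and Asthma Numeracy Questionnaire"), and two for youth (S-TOFHLA and WIAT-III). It does not say which is used for Aim 3.

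**The concern.** In a two-arm trial, benefit from the PAAP is a PAAP-WAAP difference. To expect it particularly at lower literacy is to expect that difference to change with literacy. A correlation between literacy and outcome inside one arm, or pooled over arms, is a different quantity. Comparing the two arms' correlations comes closer, but a correlation mixes the slope with the spread of the data, so it does not give the size of the benefit for a family at a given literacy level.

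Literacy is the Background section's reason for a simpler plan, and Methods presents the findings as relevant to families with literacy difficulties and as a guide to further work. As planned, the effect that motivates the trial would be reported without an estimate or an interval.

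**Working it through.** The documents give no figure for Aim 3 to reproduce: no alpha, power, target effect or arm sizes. Inputs taken from them are N = 45 (Methods), two arms (Design) and the model terms listed above. Assumptions are two-sided alpha 0.05, arms of 22 and 23 (15 and 30 shown as a range), all 45 analysable, and literacy scaled to SD 1.

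**1. Equal correlations do not fix the treatment difference.** In each arm, r = slope × SD(literacy) / SD(outcome). Let WAAP have slope 0.5 and residual SD 0.866, so the total SD is 1 and r = 0.50. Three PAAP arms also have r = 0.50:

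| PAAP mean shift | PAAP slope | PAAP residual SD | Difference at -1 SD | Difference at +1 SD |
|---|---|---|---|---|
| 0 | 0.50 | 0.866 | 0 | 0 |
| 0.5 | 0.50 | 0.866 | 0.50 | 0.50 |
| 0.5 | 0.25 | 0.433 | 0.75 | 0.25 |

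The difference at literacy L is shift + (PAAP slope - 0.5) × L. No benefit, uniform benefit and benefit concentrated at low literacy all give the same pair of correlations.

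**2. Power of a between-arm comparison of correlations.** On the Fisher z scale, SE = sqrt(1/19 + 1/20) = 0.32.

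- r = 0.3 v 0: z difference 0.310, power 16%.
- r = 0.5 v 0: z difference 0.549, power 40%.
- With arms of 19 and 20 these fall to 14% and 35%.

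**3. Power of a literacy by Group term (level outcome).** With residual SD 1, SE of the slope difference = sqrt(1/21 + 1/22) = 0.305.

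- Slopes -0.5 v 0: 36% from the noncentral t on 41 df; 38% to 43% by simulation, depending on whether total or residual SDs are equal across arms.
- Slopes -0.3 v 0: about 16%.
- The slope difference detectable with 80% power is about 2.80 × 0.305 = 0.85 SD per SD of literacy.

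Steps 2 and 3 have much the same power. What the interaction adds is an interpretable estimate.

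**4. Precision of the PAAP-WAAP difference.** Half-width = t(0.975, 41) × sqrt(sum over arms of 1/n + z²/(n - 1)), in residual SDs, where z is the distance from mean literacy in SDs.

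- At the mean: 2.02 × sqrt(0.0889) = 0.60.
- At ±1 SD: 2.02 × sqrt(0.1820) = 0.86. With arms of 15 and 30: 2.02 × sqrt(0.2059) = 0.92.
- For a change score, multiply by sqrt(2(1 - c)), where c is the baseline to follow-up residual correlation. For c = 0.7, 0.5 and 0.3 this gives 0.67, 0.86 and 1.02.
- For a binary outcome at one time point, SE = sqrt(0.1820 / (p(1 - p))). At p = 0.5, exp(1.96 × 0.853) = 5.3; at p = 0.3, exp(1.96 × 0.931) = 6.2. The odds ratio is known to within a factor of about 5 to 6 either way.

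**The case against.** The strongest reply is that the plan does what the aim asks. Aims 1 and 2 each state a working hypothesis against the written plan; Aim 3 states an association objective and then an expectation that names no comparator. The correlations meet that objective. The between-groups wording can fairly be read as comparing correlations across arms, which is a look at modification with about the same power as an interaction. The Study Analysis Plan models mainly serve Aim 1, so their lack of a literacy term does not cancel Aim 3's own method. This is also a pilot about acceptability and feasibility, and no primary conclusion changes.

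Most of this stands. A reader might infer that Aim 3 has no valid analysis, or that modification is ignored altogether; the documents support neither reading. What remains is that the comparison is undefined and, even read generously, cannot show how much the PAAP helps at low literacy.

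A reader might also infer that a significant correlation within one arm will be presented as differential benefit. That would be a serious error for outcomes analysed as levels. With literacy equally prognostic in both arms and no differential benefit, an arm of 22 or 23 gives a significant correlation 28% of the time at r = 0.3 and 68-71% at r = 0.5 (simulation). Nothing in the documents says correlations will be read that way, so these figures do not measure a fault in the plan. They also do not carry over to ACT and spirometry change scores. If literacy is equally prognostic at baseline and follow-up, the corresponding rate there is about 5%.

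**Conclusion.** The point holds in limited form. The planned correlations answer Aim 3's formal objective. Its expectation of particular benefit at lower literacy is matched only by an undefined, indirect comparison of correlations that depends on each arm's variances and returns no PAAP-WAAP difference or interval at any literacy level. Reading the expectation as a literacy-dependent PAAP-WAAP difference is an interpretation, though the natural one in a two-arm trial.

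A better analysis is available from data already collected, so the change is worth making. It gains interpretability rather than power. The figures rest on the assumed 22/23 split and complete data; the documents give neither the split nor analysable numbers by outcome, and fewer participants would widen every interval. The power figures are for level outcomes, and none was calculated for the three-way term on ACT and spirometry.

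**What to change.** 1. Name one continuous baseline literacy score for the caregiver and one for the youth.
2. Replace the between-groups comparison of correlations with a literacy by Group term in the continuous-outcome models, labelled exploratory and post hoc because data collection ended in May 2018. Where a baseline exists (ACT and spirometry), use literacy by Group by Time with its lower-order terms. Methods lists no pre-intervention knowledge interview, and adherence monitoring starts at baseline, so use post-randomisation levels for knowledge and adherence unless an undescribed earlier measurement exists.
3. Keep the existing endpoint rule, "Pre-post analysis included combining 3 month and 6 month time points for outcome measures", so that families whose last visit was at 3 months stay in.
4. Extend the term to the ordinal adherence and binary ACT models only if they remain estimable. The adherence model already carries an unstructured matrix and a prescription interaction or stratification. Report odds ratios there.
5. Report the PAAP-WAAP difference with 95% CI at low and high literacy, for example 1 SD below and above the mean, without significance claims. State how many scores and outcomes were examined: two scores across knowledge, adherence, ACT, spirometry and satisfaction already make 2 × 5 = 10 sets of estimates.
6. Keep within-arm correlations as descriptive, and limit conclusions from them to association.

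The cost is revised Aim 3 wording and several added terms per model: literacy and its interaction with Group where the outcome is a level, and four terms (literacy, literacy by Group, literacy by Time and the three-way term) where there is a baseline. No new data are needed. The estimates will be wide, and their use is to show that width to whoever plans the next trial.
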